There has been growing interest in the use of long-acting local anesthetics for improving pain control in orthopaedics⁷, particularly in the elective total joint arthroplasty population⁸. Studies have shown that arthroplasty patients receiving long-acting local anesthetics have decreased opiate requirements, reduced length of stay, and lower costs⁸⁻¹². Although well-demonstrated in the elective arthroplasty population, the effects of long-acting local anesthetics have yet to be demonstrated in the hip fracture population. Given that these fractures frequently occur in medically frail patients with multiple comorbidities^{13,14}, in whom post-operative confusion and delirium are relatively common^{15,16}, there is the potential for treatments that decrease opiate requirements to demonstrate substantial medical and economic benefits.

Exparel (liposomal bupivacaine) and long-acting local anesthetics have been used extensively in hip replacement surgery and have not been shown to be associated with any increased risks¹⁷⁻²³. In the case of patients with displaced femoral neck fractures treated with arthroplasty, the surgical techniques are identical to those being used in this study. Exparel has also been used in trauma surgery²⁴ as well as foot and ankle surgery²⁵ without any increased described risks, although its use explicitly in hip fractures has not been published. However, the PI has trained in other medical centers where Exparel is routinely used in hip fracture patients without any identified increased risks or complications, but there is a paucity of data on this subject, which is the rationale for this study.

We hypothesize that in patients with osteoporotic fragility fractures of the hip, patients receiving intraoperative long-acting local anesthetics will have decreased pain and decreased post-operative opiate requirements, leading to less delirium and decreased hospital resource utilization during their index hospitalization.

5. Inclusion and Exclusion Criteria

Inclusion Criteria

- Age 55 or older
- Sustaining either an OTA/AO type 31A or 31B fracture undergoing ORIF or hemiarthroplasty
- Able to consent
- Isolated injury

Exclusion Criteria

- OTA/AO 31B1 (Impacted/slightly displaced)
- Baseline dementia or cognitive deficit
- Inability to consent

- Chronic Opioid use
- End stage liver disease with Model for End-Stage Liver Disease (MELD) greater than 20.

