- End stage renal disease as defined by patients requiring hemodialysis at least twice weekly
- Polytrauma, defined as:
 - Concurrent upper or lower extremity fracture, pelvis fracture, spine fracture, rib fractures, or facial fractures
 - Blunt chest or abdominal trauma resulting in diagnosed organ injury
 - Head trauma resulting in intracranial bleed or diagnosed concussion
- Allergy to amide-type local anesthetics
- Prisoners (unlikely to be accessible for follow-up)

6. Study-Wide Number of Subjects

This is a multi-center study being conducted in conjunction with the University of Kentucky. The total recruitment goal is 60 patients, with a goal enrollment of 30 patients at University of Massachusetts, and 30 patients at University of Kentucky.

Recent studies evaluating regional nerve blocks in hip fractures have shown an average morphine sulfate equivalent of 3.5 +/- 0.52 mg/d in the first 3 postoperative days²⁶. That same study showed a 33% reduction in morphine equivalents (3.5 mg/d vs 2.1 mg/d). Assuming a similar effect size, this study would require only 8 patients group to be powered to 80% with a significance level of 0.05. With a target recruitment goal of 50 patients, the study would be powered to detect differences as low as 0.42 mg/d (a 12% effect size). Assuming a 10-20% loss to follow-up, we aim to recruit a total of 60 patients studywide (i.e. 30 at each site).

7. Study-Wide Recruitment Methods

Recruitment methods will be the same at both University of Massachusetts and University of Kentucky. Refer to [24. Recruitment Methods](#) for details of recruitment methods at University of Massachusetts.

8. Study Timelines

- Duration of an individual subject's participation in the study

An individual subject's participation in the study begins at enrollment and ends after the 30 day post-op follow-up period.

- Duration anticipated to enroll all subjects

From recent internal data review, we treat between 250-300 hip fractures annually at UMMMC. We anticipate 10-25% of patients will be both eligible and willing to enroll in the study, so to enroll 30 patients should take 6-12 months.

- Estimated date for the investigators to complete this study (complete primary analyses)

Primary analysis should be completed once the final cohort of patients complete their 30 day study window, so we expect 13-14 months after initiation of enrollment.

9. Study Endpoints

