- **Primary Outcome Variables:** Total morphine equivalents in the post-operative period for 24, 48, and 72 hours, CAM score and average Pain Visual Analog Scale
- **Secondary Outcome Variables:** Length of stay, discharge disposition, timing and participation with inpatient physical therapy, complications and 30 day readmission.

10. Procedures Involved

- **Patient identification:** Patients will be identified on morning intake rounds by the trauma team and the research staff who are present daily to screen and enroll patients.
- **Screening/Enrollment:** The research staff will review the charts to identify patients meeting the inclusion/exclusion criteria. Patients will be approached for study participation and enrolled in the study prior to surgery. For potential participants, the research staff will interview the patients, confirm willingness to participate and inclusion/criteria.
 - We will utilize a Mini-COG (Screening for Cognitive Impairment in Older Adults)²⁷. A score of <4, which has been shown to have high sensitivity for dementia screening will define cognitive impairment and will preclude enrollment.
 - At time of enrollment, preoperative demographics will be recorded which will include age, sex, comorbidities, current use of anti-epileptic/anti-depressive medications for pain control, type of surgical approach, pre-ambulatory status and implant class.
 - After this review and screening, the patient will be given the opportunity to ask researchers questions about the study. It will be reiterated to all patients during preoperative discussions that their enrollment status in no way will affect their ability to get adequate post-operative pain control.
- **Randomization:** Randomization will be done through the research pharmacy. Participants will undergo block randomization (block size: 10) through a computer-generated algorithm.

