- **Treatment:** Surgical treatment will be performed according to the attending surgeon and is independent of the study. At the conclusion of surgery, they will receive a subcutaneous injection of either Exparel placebo. Patients will receive operative treatment of the hip fracture per the operating surgeon. At the conclusion of surgery, Exparel will be given in 20cc doses, diluted with 40cc of normal saline to make 60cc of total injection volume. The injection solution contains a total of 266mg free base bupivacaine (equivalent of 300 mg bupivacaine HCl). The research pharmacy will prepare the injection solution to contain either Exparel or placebo solution. In intra-capsular arthroplasty cases, the solution will be injected circumferentially into the capsule, surrounding musculature, and subcutaneous layer. In cases with extra-capsular fractures treated with sliding hip screws or cephalomedullary nails, the solution will be administered in the deep tissue and muscles around the fascial incisions as well as in the subcutaneous layer. At the time of medicine or placebo administration, the operating room circulating nurse will create a log entry for Exparel administration in the medication administration record (MAR). This is the section of the medical record where all medications must be recorded, and will be consulted prior to delivery of any other local anesthetic agents, which will serve to limit the additional exposures and minimize the risk of toxicity.
- **Post-operative inpatient care:** While admitted to the hospital, patients will receive medical care per routine, including a standardized post-operative pain control regimen. Post-operatively, all patients will receive a uniform pain control protocol consistent with the current standard of care. We have worked with our anesthesia team to create a consensus-driven protocol to ensure patients are

evaluated for pain and having pain treated in an appropriate and uniform manner. The written protocol is included at the conclusion of this document as Appendix A. We will collect the following data from inpatient hospitalization.

- As a part of the research study regiment, delirium will be assessed using the Confusion Assessment Method (CAM)²⁸, which will be administered 6 hours following surgery, post-operative day 1, 2 and 3 between 8AM-12PM, when a provider is called to the bedside to evaluate the patient for confusion, and also by nursing staff at each nursing shift (Q12).

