Following initial enrollment, each patient will be assigned a unique patient identifier. All electronic documentation containing total morphine equivalents, visual analogue scores and all other medical information will be associated with this unique patient identifier during analysis. All protected health information will be stored in a separate, password-protected research file that will not be accessed regularly. Following our secondary analysis, all personal health information will be removed from our electronic files and destroyed in accordance with patient privacy guidelines.

Data obtained at UMMC during the study will be recorded and stored using Redcap software that will be maintained at the hospital by the research staff. The University of Kentucky will be responsible for their own data infrastructure. Upon conclusion of the study, the University of Kentucky will share de-identified data (with information relating to the study endpoints) with the University of Massachusetts

for final analysis. Final analysis will be conducted using Excel spreadsheets. All documents will be stored on a password-protected research drive and only research personnel will have access to its content. Paper documents, including consent forms, will be stored in a locked cabinet in a secure research room.

Each researcher on the project has passed the CITI exam on ethical conduct of research and has received training and supervision regarding patient confidentiality. Only approved research personnel will administer consents and perform phone surveys. All efforts will be made to maintain the confidentiality of the patient reported data. Only study personnel listed in eIRB will have access to identified study data.

Consistent with other research projects through the UMass Orthopedic Trauma Center, all other research-related files including but not limited to copies of consents and surveys will be stored on a password protected research drive or locked research cabinet. Research personnel also have allocated space with locked drawers for source document files and secure workspace apart from patient or public areas that is also locked.

13. Provisions to Monitor the Data to Ensure the Safety of Subjects

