Official Title: Does the Use of Liposomal Bupivacaine Decrease Narcotic Requirements in Geriatric Hip Fractures? A Randomized, Double Blinded Control Trial

NCT Number: NCT03289858

Date of Document: August 27, 2017

Statistical Analysis Plan for Randomized Controlled Trial for Exparel Hip Fracture (H00013594)

Primary Outcome Variables: Total morphine equivalents in the post-operative period for 24, 48, and 72 hours, CAM score and average Pain Visual Analog Scale

Secondary Outcome Variables: Length of stay, discharge disposition, timing and participation with inpatient physical therapy, complications and 30 day readmission.

Comparisons between continuous variables will be made using Students t-test, and categorical variables using the Chi-square statistic or Fischer's Exact Test, based on incidence.

Power analysis: Recent studies evaluating regional nerve blocks in hip fractures have shown an average morphine sulfate equivalent of 3.5 +/- 0.52 mg/d in the first 3 postoperative days. That same study showed a 33% reduction in morphine equivalents (3.5 mg/d vs 2.1 mg/d). Assuming a similar effect size, this study would require only 8 patients group to be powered to 80% with a significance level of 0.05. With a target recruitment goal of 50 patients, the study would be powered to detect differences as low as 0.42 mg/d (a 12% effect size)

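### Site and procedure class are known for every patient but unused: a pre-specified adjusted model is a cheap optional gain over the (valid) unadjusted t-test, with useful precision only if the two factors explain roughly 10% of variance or more

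*SAP*

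**What the plan says.** The SAP's only statement of method is "Comparisons between continuous variables will be made using Students t-test, and categorical variables using the Chi-square statistic" (or Fisher's exact test when counts are low). Neither document names a covariate, an adjusted model or a stratification factor.

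The Protocol nevertheless has two candidate factors to hand:

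- **Site.** Section 6 plans two centres, "with a goal enrollment of 30 patients at University of Massachusetts, and 30 patients at University of Kentucky".
- **Procedure class.** Section 5 admits patients "Sustaining either an OTA/AO type 31A or 31B fracture undergoing ORIF or hemiarthroplasty", and section 10 lists "type of surgical approach, pre-ambulatory status and implant class" among the items recorded at enrolment.

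Neither factor can be altered by allocation. Section 10 says "Surgical treatment will be performed according to the attending surgeon and is independent of the study", and of the study injection, "At the conclusion of surgery, they will receive a subcutaneous injection".

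On randomization, section 10 says only "Participants will undergo block randomization (block size: 10) through a computer-generated algorithm"; it does not say whether blocks run separately at each site. On data transfer, section 12 says "the University of Kentucky will share de-identified data (with information relating to the study endpoints").

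**The concern.** Any difference in opioid use or pain between the two sites, or between arthroplasty and fixation, stays in the t-test's error term and widens the CI for the treatment effect. A linear model with both factors removes that part of the error at the price of two degrees of freedom and some loss from chance imbalance.

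Blocking adds a second reason. If blocks run within site, the design balances site across arms, but the unadjusted t-test still counts site differences as noise. It is then conservative whenever site matters.

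Precision near the plan's detectable limit is at stake, not the validity of the result. Pre-specification matters because covariates chosen after the data are seen invite selective reporting.

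**Working it through.** **Inputs from the documents.** SD 0.52 mg/d, control mean 3.5 mg/d, planned effect 3.5 − 2.1 = 1.4 mg/d, 50 patients, 80% power, alpha 0.05 and detectable difference 0.42 mg/d (SAP, power analysis); 60 recruited, 10–20% loss (Protocol section 6).

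**Assumptions.** Two-sided test; 25 patients per arm; ± read as an SD; 10 of 60 lost (16.7%); R² for site and procedure together varied from 0 to 0.20, because the documents give no value.

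**1. The plan's own figure.** SE = 0.52 × √(2/25) = 0.147. With the noncentral t on 48 df, the difference detectable at 80% power is 0.4205 mg/d, and power at 0.42 is 79.9%. The stated 0.42 mg/d (0.42/3.5 = 12%) reproduces.

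**2. The planned effect.** For 1.4 mg/d, 8 per arm already gives 99.9% power. At 25 per arm adjustment has nothing to add.

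**3. Break-even.** With q covariate degrees of freedom and allocation not balanced on them, the variance of the adjusted estimate relative to the t-test is (1 − R²)(N − 3)/(N − 3 − q). Setting this to 1 gives R² = q/(N − 3).

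- Two binary factors, N = 50: 2/47 = 4.3% (4.2 to 4.5% depending on whether degrees of freedom, variance or CI width is compared).
- Two binary factors, N = 60: 2/57 = 3.5%.
- Three procedure levels, N = 50: 3/47 = 6.4%.
- Blocks run within site, N = 50: site is nearly balanced, and simulation puts the CI-width break-even at about 2.6%.

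If the factors have equal shares and each splits patients 50/50, the difference per factor is 2 × 0.52 × √(R²/2). That is 0.12 mg/d at 2.6%, 0.15 at 4.3%, 0.23 at 10% and 0.33 at 20%.

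**4. Gain or loss at N = 50, two binary factors.** The SE ratio, power and detectable difference use the formula in step 3. The CI columns come from simulation (20,000 trials per setting; ranges span blocks within or not within site and a 50/50 or 70/30 procedure mix).

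| Assumed R² | SE ratio | Power at 0.42 mg/d (t-test 79.9%) | Detectable mg/d (t-test 0.421) | Mean CI width | Trials where adjusted CI is wider |
|---|---|---|---|---|---|
| 0 | 1.022 | 78.1% | 0.430 | 1.4–2.3% wider | 76–82% |
| 0.05 | 0.996 | 80.1% | 0.419 | 0.3–1.3% narrower | 43–52% |
| 0.10 | 0.970 | 82.2% | 0.408 | 3.0–3.9% narrower | 23–30% |
| 0.20 | 0.914 | 86.4% | 0.385 | 8.6–9.5% narrower | 5–8% |

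The percentage change in CI width depends on R² and N, not on the SD, so the same table serves average VAS at whatever R² applies there.

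**5. Conservatism.** Under no treatment effect, with R² = 0.20 and blocks within site, the t-test rejected in 4.1% of 40,000 simulated trials and the adjusted model in 5.0%. Without blocking by site the rates were 5.1% and 5.2%.

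**6. Skewed totals.** Appendix A gives opioids in stepped, as-needed doses, so skew is plausible. Assumed scenario: median 10.5 mg, log-SD 0.6, 0.8 or 1.0, 5% zeros, 40% reduction, and site and procedure effects of 0.4 on the log scale (about 1.5-fold each).

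| Log-SD | t-test power | Adjusted linear | Adjusted rank |
|---|---|---|---|
| 0.6 | 61% | 65% | 69% |
| 0.8 | 39–40% | 40–42% | 47–48% |
| 1.0 | 24–25% | 25% | 33–34% |

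The linear model gains about 0 to 4 points here, and loses 0.6 to 2.4 points if the two factors have no effect. The rank column combines the benefit of ranking with that of the covariates.

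**The case against.** The strongest reply is that nothing is broken. Randomization makes the unadjusted comparison unbiased, its type I error is held, and leaving out covariates in a trial of 50 to 60 patients is a legitimate choice. No passage shows that site or procedure predicts opioid use or pain, and the uniform pain regimen in section 10 may shrink site differences. The gain also lies near 0.42 mg/d, not at the 1.4 mg/d the trial is sized on. All of this stands, and it is why the point is optional.

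A reader might infer more than the documents support:

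- **That the t-test is invalid or biased.** It is neither; at most it is conservative, and only if blocks run within site and site matters.
- **That adjustment will raise power.** That needs an R² the documents do not give. Different infiltration techniques for arthroplasty and fixation (section 10) make a procedure effect plausible but do not show one.
- **That a few percent of explained variance is enough.** A break-even below 3% requires blocks within site, which section 10 does not state. At 5% the adjusted CI is the wider one in about half of trials.
- **That Kentucky will not send procedure class.** Section 12 says the shared data include endpoint information; it does not say covariates are left out. The field needs confirming, not presuming absent.

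**Conclusion.** The point holds as a low-cost improvement. The plan leaves two recorded, allocation-independent factors out of the analysis of its continuous primary outcomes. Under a normal outcome with 50 analysed patients and one degree of freedom per factor, adjustment is roughly neutral up to an R² of about 5% and worthwhile from about 10%. The possible loss is small and bounded; the possible gain is moderate and unproven. Splitting procedure into three levels moves break-even to about 6%, and strong skew removes most of the linear model's advantage for opioid totals.

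**What to change.** Add to the SAP, before unblinding:

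- For morphine-equivalent totals at 24, 48 and 72 hours and for average VAS, a linear model with arm, site and two-level procedure class (arthroplasty versus fixation). Include CAM if it is analysed as an average score, as Protocol section 3 suggests.
- The adjusted mean difference in original units with a 95% CI.
- A rank-based sensitivity analysis of the opioid totals with the same two factors.
- A statement of whether blocks run within site.
- Confirmation that procedure class is in the Kentucky transfer, coded the same way at both sites.

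**Cost.** Residual degrees of freedom fall from 48 to 46. With chance imbalance, that is the 1 to 2 power points and 1.4 to 2.3% of CI width shown at R² = 0. Otherwise it takes a few lines of text and, at most, one extra transferred field. No new data collection is needed, and the linear model can be fitted in Excel, the tool named in Protocol section 12.
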